4.3.8.3 Vital signs

Blood pressure baselines are defined as the average of all measurements from the screening visits and randomization visit. For subjects on hemodialysis, vital signs should be recorded pre-dialysis. For subjects on peritoneal dialysis, vital signs may be recorded at any time during the visit.

Descriptive statistics for vital signs (e.g., systolic and diastolic blood pressure and MAP) and their changes from baseline at each visit and at the end of study will be presented by treatment group.

Vital sign values are potentially clinically significant (PCS) if they meet both the observed value criteria and the change from baseline criteria listed in [Table 2](#) below. The number and percentage of subjects with post-baseline PCS values will be tabulated by treatment group.

Table 2 Criteria for Potentially Clinically Significant Vital Signs

Vital Sign Parameter	Flag	Criteria*	
		Observed Value	Change
Systolic Blood Pressure (mmHg)	High	≥ 170	Increase of ≥ 20
	Low	≤ 90	Decrease of ≥ 20
Diastolic Blood Pressure (mmHg)	High	≥ 110	Increase of ≥ 15
	Low	≤ 45	Decrease of ≥ 15
Pulse Rate (bpm)	High	≥ 120	Increase of ≥ 20
	Low	≤ 50	Decrease of ≥ 20

* A post-baseline pre-dialysis or post-dialysis value is considered as a PCS value if it meets both criteria for observed value and change from pre-dialysis or post-dialysis baseline

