1.3 Benefit/risk and ethical assessment

The primary benefit for patients randomized to roxadustat is expected to be the correction of anemia, including the relief of associated signs and symptoms and an improved quality of life. Roxadustat is expected to be at least as safe as parenteral erythropoietin analogues.

An established dose adjustment algorithm will be used during the study to titrate roxadustat doses to enable patients to achieve and maintain Hb levels, while closely monitoring the rate of rise of Hb levels. Roxadustat doses may be held and therapeutic phlebotomy is allowed in the event of excessive erythropoiesis.

Dosing of epoetin alfa in the epoetin alfa group will be consistent with approved prescribing information. Adverse and serious adverse events, and laboratory parameters including electrolytes, liver enzymes, and iron indices, will be closely monitored to ensure the safety of treatment with roxadustat or epoetin alfa.

In studies with healthy subjects, headache and dizziness were common events which occurred at a higher frequency with roxadustat compared to placebo. An increased frequency of mild to moderate musculoskeletal pain was also noted with high doses of roxadustat. These findings were not observed at the usual therapeutic dose range in the Phase 2 studies in the target populations.

Treatment with roxadustat was associated with increases in heart rate which were most pronounced at supra-therapeutic doses (5 mg/kg). At the high clinical dose of 2.75 mg/kg, the increase was modest (about 10 bpm from baseline, placebo corrected). In the Phase 2 studies, there were no adverse effects on hemodynamics with repeat dose administration in the therapeutic dose range. The cumulative safety data to date have not identified any major risks related to roxadustat, which was well tolerated by healthy subjects and patients with CKD.

The safety of treatment with roxadustat and epoetin alfa will be carefully monitored and an independent Data Safety Monitoring Board (DSMB) will perform periodic assessments of safety data to detect any potential safety signals that may arise during the study and advise the International Coordinating Investigator and Sponsor accordingly.

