4. STUDY PLAN AND TIMING OF PROCEDURES

During study visits, all assessments including laboratory tests and physical examinations should be completed prior to initiation of the hemodialysis (HD) procedure in patients receiving HD. The EQ-5D-5L quality of life assessments should be completed prior to any intervention (e.g., start of dialysis in HD patients) and at approximately the same time of the day. Blood samples for Hb measurement and safety laboratory tests will be obtained according to Study Plan, [Table 1](#).

Table 1 Study Plan

	Screening ^a		Treatment (-4d to +2d)																								EOT (-4d to +2d)	EOS (4wks after EOT+4d)	
	Up to 6 wks		Rand (wk 0)	wk 1 	Wk 2	4	6	8	10	12	14	16	18	20	24	28	32	36	40	44	48	52	56	60	every 4 wks				
Visit^o	1	2	3	4	5	7	9	11	12	13	14	15	16	17	18	19	20	21	22	23	24	25	26	27	etc				
Written informed consent	X																												
Eligibility criteria	X	X	X																										
Demographics and medical history	X																												
Physical examination	X ^b		X							X ^b					X ^b													X	
Height ^c , weight ^d	X		X							X					X			X					X				every 24 wks ^t	X	
12-lead ECG			X							X					X													X	
Blood pressure, Heart rate	X ^e	X	X ^{e,q}			X		X		X ^e		X		X	X ^e	X	X	X	X	X	X	X	X ^e	X	X		X, every 24 wks X ^{e,t}	X ^e	
Renal ultrasound if none performed within 12 weeks prior to randomization		X																											
Serum hCG pregnancy test ^f	X		X							X				X		X		X		X		X		X			every 8 wks	X	

Table 1 Study Plan

	Screening ^a		Treatment (-4d to +2d)																								EOT (-4d to +2d)	EOS (4wks after EOT+4d)
	Up to 6 wks		Rand (wk 0)	wk 1 	Wk 2	4	6	8	10	12	14	16	18	20	24	28	32	36	40	44	48	52	56	60	every 4 wks			
Visit^o	1	2	3	4	5	7	9	11	12	13	14	15	16	17	18	19	20	21	22	23	24	25	26	27	etc			
Serology (HIV, Hepatitis B and C), Vitamin B12, folate	X																											
Hemocue assessment ^g	X	X	X		X	X	X	X	X	X	X	X	X	X	X	X	X	X	X	X	X	X	X	X	X	X	X	
Hemoglobin (Central lab)		X			X		X	X	X		X	X	X	X		X	X	X	X	X	X		X	X	X	X	X	
Complete blood count (CBC) ^h	X		X			X				X					X								X				X	

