6.3.6 Adverse events based on examinations and tests

The results from protocol mandated laboratory tests and vital signs will be summarised in the clinical study report. Deterioration as compared to baseline in protocol-mandated laboratory values, vital signs should therefore only be reported as AEs if they fulfil any of the SAE criteria or are the reason for discontinuation of treatment with the investigational product.

If deterioration in a laboratory value/vital sign is associated with clinical signs and symptoms, the sign or symptom will be reported as an AE and the associated laboratory result/vital sign will be considered as additional information. Wherever possible the reporting Investigator uses the clinical, rather than the laboratory term (e.g. anemia versus low hemoglobin value). In the absence of clinical signs or symptoms, clinically relevant deteriorations in non-mandated parameters should be reported as AE(s).

Deterioration of a laboratory value, which is unequivocally due to disease progression, should not be reported as an AE/SAE.

Any new or aggravated clinically relevant abnormal medical finding at a physical examination as compared with the baseline assessment will be reported as an AE.

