1.2 Study design

This is a Phase 3, multicenter, randomized, open-label, active-controlled study to evaluate the safety and efficacy of roxadustat compared to epoetin alfa for the treatment of anemia in dialysis subjects. Subjects on hemodialysis (HD) or peritoneal dialysis (PD) who have been treated with an erythropoietin analogue or have an indication for treatment with an erythropoietin analogue will be evaluated for eligibility and randomized at a 1:1 ratio to treatment with roxadustat (with discontinuation of prior erythropoietin analogue therapy) or to an active control group treated with epoetin alfa.

The study periods are as follows:

- **Screening Period:** Up to 6 weeks.
- **Treatment Period:** Subjects will be randomized (1:1) to open-label treatment with either roxadustat or epoetin alfa. Treatment duration is variable for individual subjects (estimated treatment up to 4 years). A common closeout will occur when the target number of MACE events has been accrued.
- **Post-Treatment Follow-Up Period:** 4 weeks from the end of treatment (EOT) visit to the end of study (EOS) visit. Subjects who discontinue study medication prematurely will be followed up for CV events, Hb measurements, vital status and hospitalizations until the end of the study (EOS), according to ITT principles, unless consent to participate is withdrawn.

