4.1.1 Censoring

For analyses based on OT+7, subjects will be censored at 7 days after last intake of study drug, or the EOS visit, whichever is earliest.

For analyses based on OT+3, subjects will be censored at 3 days after last intake of study drug, or the EOS visit, whichever is earliest.

For analyses based on OT+0, subjects will be censored at last intake of study drug, or the EOS visit, whichever is earliest.

For analyses based on the ITT analysis set and FAS, subjects will be censored at their individual EOS visit, regardless of if they have discontinued study drug or not. Complete endpoint information will be pursued with every effort for all subjects, unless they exercise their right to withdraw consent. Subjects who withdraw consent will be censored at date of withdrawal of consent, and subjects who are lost to follow up (LTFU) will be censored at last available contact.

Subjects who withdraw consent and for whom only vital status (known to be alive at study closure, or date of death) may be obtained from public records, the occurrence of all components of the primary endpoint cannot be assessed, and will thus be censored at date of consent withdrawn for all analyses. However, the determination of all-cause death will utilize all publicly known mortality data, even that extending beyond date of consent withdrawal. The vital status information will be included in the analysis of all-cause death as a single endpoint, and in sensitivity analysis and tabulations. Similarly, complete information on the endpoint may not be obtained for subjects who are LTFU. Any such subject will be censored in the analysis at the last contact where all elements of the endpoint were assessed. A subject

will not be recorded as LTFU until the end of the study, after every allowable effort to get in contact has been made. Hence, it is anticipated that the number of subjects LTFU will be limited.

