4.3.8 Safety assessment analysis

The safety analysis will be performed using the OT+7. Safety variables include adverse events (AE), laboratory variables, vital signs, ECG variables and physical examinations. For each safety variable, the last assessment made on the screening visits or the randomization visit will be used as the baseline for all analyses, unless specified otherwise.

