4.3.8.1 Adverse events

Adverse events will be coded using the Medical Dictionary for Regulatory Activities (MedDRA) version 20.0 higher.

An AE (classified by preferred term) started during the treatment period will be considered a treatment-emergent adverse event (TEAE) if it was not present prior to the first dose of study medication. An AE that starts more than 7 days after the last dose of study medication will not be counted as a TEAE.

The number, percentage and percentage per PEY of subjects reporting TEAEs in each treatment group will be tabulated by system organ class and preferred term; by system organ class; by preferred term and by system organ class, preferred term, and relationship to study medication. If more than one event occurs with the same preferred term for the same subject, the subject will be counted only once for that preferred term using the most severe and most related occurrence for the summarization by severity and by relationship to the study medication. In addition to reporting TEAEs by number of subjects, the table by system organ class and preferred term will also be reported by patient years and event rates. Thus, allowing for potential systematic differences in mean exposure between the treatment groups. The event rate for a particular AE will be derived as the number of subjects with the AE, divided by total number of days at risk for the AE across all subjects in given group, multiplied by 365.25 multiplied by 100.

The distribution of TEAEs by severity and relationship to study medication will be summarized by treatment group.

The incidence of common ($\geq 5\%$ of subjects in any treatment group) TEAEs, common treatment-emergent serious AEs (TESAE), and AEs leading to discontinuation of study medication will be summarized by preferred term and treatment group, sorted in decreasing overall (across treatments) frequency. Moreover, TEAEs leading to hospitalization by system organ class and preferred term will be presented. In addition, related deaths and fatal SAEs (i.e., events that caused death) will be summarized separately by treatment group, system organ class and preferred term. TEAEs with outcome of deaths and TESAEs will also be presented for the ITT analysis set.

TEAEs and TESAEs by system organ class and preferred term will also be reported with OT+3 and OT+0.

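### PCS vital signs are summarised only as a crude on-treatment percentage, which rises with time on drug; adding exposure-aware measures would limit distortion if exposure differs by arm

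*SAP*

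**What the plan says.** SAP 4.3.8.3 calls a vital sign PCS when it meets both an observed-value and a change criterion in Table 2: high and low flags for systolic pressure, diastolic pressure and pulse rate, six in all. The planned summary is: "The number and percentage of subjects with post-baseline PCS values will be tabulated by treatment group". No person-time, fixed window or time-to-event measure is given.

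The window is set in SAP 4.3.8 ("The safety analysis will be performed using the OT+7") and SAP 4.1.1 ("For analyses based on OT+7, subjects will be censored at 7 days after last intake of study drug", or at the EOS visit if earlier). Exposure is not fixed; SAP 1.2 says: "Treatment duration is variable for individual subjects (estimated treatment up to 4 years". In Protocol Table 1 the row "Blood pressure, Heart rate" is marked every 4 weeks from week 4.

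For treatment-emergent adverse events, SAP 4.3.8.1 also reports patient-years and event rates, with the stated purpose: "Thus, allowing for potential systematic differences in mean exposure between the treatment groups".

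Other vital-sign outputs are the by-visit descriptive summaries in 4.3.8.3 and, in SAP 4.3.5.5, an ANCOVA of change in heart rate and in systolic, diastolic and mean arterial pressure from week 28 to EOT. SAP 4.3.8.4 uses the same crude number and percentage for PCS ECG values.

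**The concern.** An ever/never percentage over unequal follow-up mixes risk with time observed. Every further 4-weekly visit on drug is another chance to cross a threshold, so at equal risk the arm that stays on drug longer shows the higher percentage. The reverse also holds: a real excess in the arm with shorter exposure can be hidden.

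Readers will compare this table by arm, because pulse rate is one of its parameters and Protocol 1.3 reports a heart-rate effect of roxadustat: "At the high clinical dose of 2.75 mg/kg, the increase was modest (about 10 bpm from baseline, placebo corrected". The next sentence of that section adds that Phase 2 repeat dosing in the therapeutic range showed no adverse haemodynamic effects.

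The adverse-event rates do not stand in for the missing measure. Under Protocol 6.3.6, deteriorations in "vital signs should therefore only be reported as AEs if they fulfil any of the SAE criteria" or are the reason for stopping drug; when there are symptoms, the symptom is what is recorded. The by-visit summaries and the ANCOVA describe levels and do not count subjects with outliers.

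**Working it through.** The plan gives no figure for PCS frequency, exposure by arm or on-drug death, so there is nothing to reproduce and every input below except the visit interval, the OT+7 window and the arm size is an assumption.

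**Inputs.** Visits every 28 days (Protocol Table 1). Window of 7 days after last intake (SAP 4.1.1). About 1000 per arm (2000 randomised 1:1, SAP 1.3). Assumed: PCS hazard h equal in both arms; exponential time on drug with mean m = 1.6 versus 2.0 years before a 4-year cap (52 visits); on-drug death L = 0.10/year, included in the total stopping rate 1/m. After the cap, mean exposure m(1 − exp(−4/m)) is 1.47 versus 1.73 years.

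**Crude percentage.** The per-visit probability is p = 1 − exp(−28h/365.25), which is 0.01522 at h = 0.2. A first PCS value at visit k counts if the subject is alive then and did not stop drug more than 7 days before:

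crude = Σ(k = 1..52) p(1−p)^(k−1) × exp(−28kL/365.25) × exp(−(1/m − L)(28k − 7)/365.25).

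With q = exp(−28/(365.25m)) this is p × exp(7(1/m − L)/365.25) × q × [1 − ((1−p)q)^52] / [1 − (1−p)q].

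- m = 1.6: q = 0.9532; 0.01522 × 1.0101 × 14.97 = 23.0%.
- m = 2.0: q = 0.9624; 0.01522 × 1.0077 × 17.29 = 26.5%.

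The false gap is 3.5 points. The 95% half-width is 1.96 × √(0.230 × 0.770/1000 + 0.265 × 0.735/1000) = 3.8 points.

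**Varying the hazard (1.6 versus 2.0 years).**

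| h per year | Crude | Gap (points) | 95% half-width |
|---|---|---|---|
| 0.02 | 2.8% vs 3.3% | 0.5 | 1.5 |
| 0.05 | 6.8% vs 8.0% | 1.2 | 2.3 |
| 0.1 | 12.8% vs 15.0% | 2.1 | 3.0 |
| 0.2 | 23.0% vs 26.5% | 3.5 | 3.8 |
| 0.4 | 37.8% vs 42.7% | 4.9 | 4.3 |

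**Varying exposure (h = 0.2).**

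- 1.8 versus 2.0 years: 1.7 points. 1.4 versus 2.0 years: 5.5 points. Equal exposure: zero.
- Closeout spread uniformly over 1 to 4 years instead of a 4-year cap for all: 19.9% versus 22.2%, 2.3 points (half-width 3.6).
- A harsher case in continuous time, with h = 0.15, discontinuation 0.40 versus 0.20/year and the same closeout spread (realised means 1.52 versus 1.92 years). Averaging h/(h+d) × (1 − exp(−(h+d)c)) over closeout time c gives 19.6% versus 24.2%. That is 4.6 points, above a half-width of 3.6.

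**Masking.** In the base case, a true hazard ratio of 1.20 in the shorter-exposure arm (h = 0.24 versus 0.20) gives 26.5% in both arms.

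**Week-52 cumulative incidence (Aalen-Johansen, death competing, stopping drug censored).** Σ(k = 1..13) p(1−p)^(k−1) × exp(−28kL/365.25) = 17.2% at h = 0.2. The expression does not contain m, so both arms agree. It does depend on L: 17.6% at 0.05/year and 16.7% at 0.15/year, so unequal on-drug death alone could leave 0.9 points.

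**Where the added measures fall short.** These results come from simulation with 400,000 per arm and 40% of subjects at hazard 1/year, the rest at zero.

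- Stopping unrelated to risk: crude 24.2% versus 26.2%; week-52 incidence 24.1% versus 24.0%; rate 21.1 versus 19.8 per 100 patient-years. The rate shows a false excess in the shorter arm.
- High-risk subjects in the shorter arm stop 1.5 times as fast: crude 20.7% versus 26.3% (5.6 points off); week-52 incidence 22.3% versus 24.2% (1.9 off).
- Twice as fast: crude 18.2% versus 26.3% (8.1 off); week-52 incidence 20.8% versus 24.2% (3.4 off).

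**The case against.** The strongest reply is that the trigger is hypothetical. A reader might infer that exposure will be shorter on roxadustat, because a need for repeat ESA rescue is a stopping reason for that arm only (Protocol 3.9.2). The documents do not support that inference: the rescue criteria in Protocol 7.7.4.2 are strict, no frequency is given, and no exposure by arm is stated. The adverse-event tables will also show patient-years by arm, so a reader can see any imbalance. This stands, and it makes the point conditional.

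A reader might also infer that a heart-rate effect could go unseen. That is not supported either. The by-visit summaries compare arms at fixed times, the SAP 4.3.5.5 ANCOVA addresses the mean shift, and hypertensive emergencies are separately adjudicated (Protocol 5.2.1). None of these counts PCS subjects per unit time, so a narrow gap remains.

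On size, much of the objection stands. Pulse flags need both an extreme value and a change of at least 20 bpm, so low hazards and gaps of 0.5 to 1.2 points are plausible. A shorter closeout spread reduces the base case to 2.3 points. Crude n (%) is also a common and defensible format for outlier tables, and SAP 4.2.2 makes everything outside the confirmatory sequence descriptive.

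**Conclusion.** The point holds in a limited form. The direction is certain: a crude on-treatment percentage rises with time on drug, and this table lacks the exposure step that the SAP uses for adverse events. The size is not known. Under the assumptions above it is about 0.5 to 5 points at mean 1.6 versus 2.0 years. It stays below chance error at 1000 per arm except at the highest hazard tried, and it vanishes if exposure is equal. Only larger exposure contrasts, such as 1.4 versus 2.0 years or a doubled discontinuation rate, clearly exceed chance error.

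It would be too strong to conclude that a week-52 cumulative incidence makes the arms comparable. That needs stopping to be unrelated to PCS risk and on-drug death to be similar by arm. No confirmatory test is affected. This is an optional improvement, best fixed before database lock so that the adjustment is not chosen after exposure by arm is known.

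**What to change.** In SAP 4.3.8.3 keep n (%). For each of the six Table 2 flags, add by arm:

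- subjects with a first PCS value per 100 patient-years at risk, using the SAP 4.3.8.1 formula;
- the cumulative incidence of a first PCS value at week 52, censored at OT+7 or EOS, with on-treatment death as a competing event.

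Apply the same to the PCS ECG table in SAP 4.3.8.4, so that the two outlier tables follow one method. Expect less effect there: Table 1 schedules post-baseline ECGs only at weeks 12, 24 and EOT, so the week-52 figure would rest mainly on two visits.

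State the limits beside the tables. The measures reduce exposure-related distortion but do not remove it. They assume that stopping drug is unrelated to PCS risk and that on-drug death is similar by arm. The rate also assumes a roughly constant hazard, and the week-52 figure omits later outliers, which remain visible only in n (%) and the rate.

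The cost is small. No new data are needed; for vital signs it is 6 flags × 2 measures × 2 arms = 24 estimates and one first-event derivation per flag, plus the matching ECG rows.

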4.3.8.4 Electrocardiogram

QTc interval will be calculated using both Bazett ($QTcB = QT/(RR)^{1/2}$) and Fridericia ($QTcF = QT/(RR)^{1/3}$) corrections; and if RR is not available, it will be replaced with 60/HR in the correction formula.

Box plots for each variable versus visit will be produced by treatment group (roxadustat vs. epoetin alfa).

ECG values are PCS if they meet or exceed the upper limit values listed in [Table 3](#) below. The number and percentage of subjects with post-baseline PCS values will be tabulated by treatment group. The percentages are to be calculated relative to the number of subjects with available baseline and at least one post-baseline assessment. The numerator is the total number of subjects with at least one post-baseline PCS ECG value.

Table 3 Criteria for Potentially Clinically Significant ECG

ECG Parameter	Unit	High Limit
QRS interval	Msec	≥ 150
PR interval	Msec	≥ 250
QTc interval	Msec	> 500 ; Change from baseline > 30 and > 60

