3.2 Safety assessments

Safety will be further assessed by evaluating the following:

- Occurrence of treatment emergent adverse events (TEAEs) and treatment emergent serious adverse events (TESAEs)
- Changes from baseline in vital signs and physical examinations.
- Mean change from baseline in clinical laboratory values.
- Occurrence of clinically significant changes from baseline in vital signs and ECG values.

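### For QRS, PR and absolute QTc >500, the ECG outlier table in SAP 4.3.8.4 does not separate new from pre-existing abnormalities, so it does not match the change-from-baseline variable in SAP 3.2

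*SAP*

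**What the plan says.** SAP 3.2 lists among the safety assessments "Occurrence of clinically significant changes from baseline in vital signs and ECG values". Protocol 2.2 likewise gives changes in ECG as a secondary safety outcome.

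SAP 4.3.8.4 turns this into a table. The definition is "ECG values are PCS if they meet or exceed the upper limit values listed in" Table 3, which gives QRS at least 150 msec, PR at least 250 msec and QTc above 500 msec. QTc alone has further entries: "Change from baseline > 30 and > 60". The numerator is set by "The numerator is the total number of subjects with at least one post-baseline PCS ECG value", and for the denominator "The percentages are to be calculated relative to the number of subjects with available baseline and at least one post-baseline assessment". The only other ECG display in that section is a box plot of each variable by visit and arm.

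Neighbouring sections treat baseline differently. For vital signs (SAP 4.3.8.3), "Vital sign values are potentially clinically significant (PCS) if they meet both the observed value criteria and the change from baseline criteria". For physical examination (SAP 4.3.8.5), a baseline-versus-last-observation shift table is planned. For adverse events (SAP 4.3.8.1), an event counts as treatment-emergent only if it was absent before the first dose.

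**The concern.** For three rows of the table, baseline enters only as a requirement that a value exists. A subject with a long-standing wide QRS needs a single post-baseline ECG over 150 msec to be counted. The row therefore mixes two groups: subjects who crossed the limit after starting treatment and subjects who were over it when randomized. Only the first group fits the variable named in SAP 3.2.

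Subjects of the second kind can enter. Protocol 3.2 sets no QRS, PR or QTc limit. It excludes infarction only within 12 weeks of randomization and heart failure only at NYHA class III or IV. SAP 1.2.3 uses a history of infarction, coronary bypass or congestive cardiac failure as a covariate, so such patients are expected in the trial.

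What is at stake is sensitivity. Pre-existing cases add roughly equal counts to both arms and pull the ratio of percentages towards 1. A reader looking for a conduction or repolarisation signal would see it weakened.

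**Working it through.** **Wording check, row by row (Table 3 with the counting rule)**

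| Row | Uses the subject's own baseline? | Counts a subject over the limit at entry who stays there? |
|---|---|---|
| QRS ≥150 | No | Yes |
| PR ≥250 | No | Yes |
| QTc >500 | No | Yes |
| QTc change >30, >60 | Yes | No, a high baseline alone does not meet it |

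The information needed to separate the two groups is already collected. The study plan (Protocol, Table 1) has an ECG at randomization, and SAP 4.3.8 states that "the last assessment made on the screening visits or the randomization visit will be used as the baseline for all analyses".

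**Size**

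The plan states no ECG outlier rate, baseline prevalence or ECG power, so there is no figure to reproduce. The following is an illustration.

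From the documents: about 2000 subjects randomized 1:1 (SAP 1.3), so about 1000 per arm.

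Assumed:
- b, the share over the limit at baseline, equal in both arms: 2%, 5% or 10%.
- New onset among the rest: 1% on epoetin alfa, 2% on roxadustat, a true ratio of 2.0. The direction is arbitrary.
- Every subject over the limit at baseline is over it again at least once afterwards.

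Formulas, with p the new-onset rate in an arm:
- Tabulated rate = b + (1 − b) × p
- Tabulated difference = (1 − b) × (2% − 1%)
- z = difference / √[(p₁(1 − p₁) + p₂(1 − p₂)) / 1000], using the tabulated rates
- For the restricted comparison, z uses 1% and 2% with 1000 × (1 − b) per arm

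Example at b = 5%: epoetin alfa 0.05 + 0.95 × 0.01 = 5.95%; roxadustat 0.05 + 0.95 × 0.02 = 6.90%; ratio 6.90 / 5.95 = 1.16; difference 0.95 points.

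| b | Epoetin alfa | Roxadustat | Ratio, SAP rule | Difference (points) | z, SAP rule | z, below limit at baseline only |
|---|---|---|---|---|---|---|
| 0% | 1.00% | 2.00% | 2.00 | 1.00 | 1.84 | 1.84 |
| 2% | 2.98% | 3.96% | 1.33 | 0.98 | 1.20 | 1.82 |
| 5% | 5.95% | 6.90% | 1.16 | 0.95 | 0.87 | 1.79 |
| 10% | 10.90% | 11.80% | 1.08 | 0.90 | 0.63 | 1.75 |

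Restricting to subjects below the limit at baseline keeps the ratio at 2.0 for every b. The z values only gauge signal against noise, since the SAP plans no test here.

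**Sensitivity to the assumptions**

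With new onset of 2% versus 4% and full persistence, the SAP-rule ratio is 1.80 at b = 0.5%, 1.49 at 2%, 1.28 at 5% and 1.15 at 10%. If only 80% of baseline abnormalities recur, the ratio at b = 5% is 1.32 instead of 1.28. In this setting pre-existing cases make up 20% (epoetin alfa) and 11% (roxadustat) of counted subjects at b = 0.5%, but 85% and 74% at b = 10%. The pattern is stable; its size is not.

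**The case against.** The case for leaving the table alone has several parts.

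- **QTc is mostly handled.** The change entries above 30 and above 60 msec measure each subject against his or her own baseline. This stands, and it limits the point to QRS, PR and the single QTc >500 row. A reader might infer that the whole ECG table fails to measure what SAP 3.2 describes; the QTc change entries show that it does not fail as a whole.
- **Adverse event tables give another route.** Protocol 5.2.4.1 has clinically significant ECG abnormalities reported as adverse events, and SAP 4.3.8.1 excludes events present before the first dose. This stands in part. That route depends on the investigator's judgement and does not replace a numeric outlier count.
- **The table is descriptive.** SAP 4.2.2 treats everything outside the confirmatory sequence descriptively, and 4.3.8.4 plans counts and percentages, with no ratio and no test. This stands and keeps the point minor. In the illustration z is below 1.96 even with no pre-existing cases, so no formal conclusion would change.
- **Randomization balances pre-existing cases on average.** This stands. A reader might infer a bias for or against roxadustat, but nothing in the documents supports one. The expected effect is a diluted ratio and lost precision.
- **The illustration assumes full persistence and one prevalence for three different limits.** This is fair, particularly for QTc >500, where one extreme reading may not recur. It affects the size and leaves the mismatch in definition untouched.
- **Restricting the table would lose information.** Removing subjects already over the limit would hide further worsening in them. This stands as an argument for adding rows and against replacing them.

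**Conclusion.** The point holds for three rows: QRS ≥150, PR ≥250 and absolute QTc >500. These rows count pre-existing and new abnormalities together and so do not match the variable in SAP 3.2. For QRS and PR, no output specified in SAP 4.3.8.4 shows within-subject change.

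Under the stated assumptions (1% versus 2% new onset, full persistence, baseline prevalence 2% to 10%), a ratio of 2.0 would be displayed as something between 1.33 and 1.08. The absolute difference would fall only from 1.0 to between 0.98 and 0.90 percentage points.

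It is tempting to go further and say that pre-existing abnormalities overwhelm the new ones. The documents give neither the baseline prevalence nor a new-onset rate, and across the assumptions tried the pre-existing share runs from a small minority to a large majority. Dilution is as far as the documents allow.

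One reading matters. Table 3 does not say whether the QTc change entries stand alone or combine with >500. They are taken here as separate. If they were meant jointly, the QTc entry would already need a change from baseline, and the point would reduce to QRS and PR.

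**What to change.** In SAP 4.3.8.4:

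1. Keep the existing all-subjects rows, so that subjects abnormal at baseline remain visible.
2. Add treatment-emergent PCS rows for QRS, PR and QTc >500. Restrict both numerator and denominator to subjects whose baseline value does not meet the limit (QRS <150, PR <250, QTc ≤500 msec).
3. Add a shift table of baseline category against worst post-baseline category for the same limits, by arm.
4. Leave the QTc change >30 and >60 rows unchanged.

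The cost is a few lines of SAP wording and a little more tabulation, with no new data. The added rows have slightly smaller denominators (for example 950 per arm instead of 1000 at an assumed 5% prevalence). They do not show further worsening in subjects already over a limit, and a shift table on the same cut-offs does not show it either.
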